5.2 Secondary Endpoints

Secondary Endpoints
1. The percentage of patients who receive safe and successful placement of the multipolar lead in the left and right phrenic nerve utilizing ultrasound guidance will be determined.
2. Phrenic nerve stimulation in synchrony with Mechanical Ventilation (MV) breaths will be measured to verify that occurs with inspiration.
3. The percentage of patients who experience one or more serious device/procedure-related adverse events during the study will be reported.

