11.2 Index Procedure

Once the study subject or authorized representative signs an ICF and his/her eligibility to participate in the study is confirmed, the PEPNS System procedure can be initiated. A primary operator will be performing the PEPNS System procedure, but an additional qualified operator may be present or assisting. A Stimdia representative may also be present during index procedure to provide technical guidance to the primary operator.

The Investigator will follow the procedure technique outlined in LM0001, PEPNS System Operator's Manual.

Prior to the start of electrical stimulation, the subject's diaphragm thickness may be measured using ultrasound and the subject will have a 12 lead ECG. In addition, baseline standard blood gasses such as pH and paO_2 , paCO_2 , SaO_2 , HCO_3 etc. and exhaled gas analysis such as end-tidal CO_2 data will be garnered for up to 24 hours prior to stimulation.

A four pole pacing lead electrodes will be percutaneously placed beside the phrenic nerves using ultrasound guidance and the ultrasound screen shots will be captured if possible. The ease of gain pacing lead access and setup will be assessed and logged.

The subjects phrenic nerve(s) will then be electrically stimulated for up to 48 hours and device and procedure information, ventilation and PEPNS System stimulation will be recorded. In addition, patient vital signs including heart and respiratory rate, blood pressure, temperature, pH, paCO_2 , paO_2 , hematocrit, end-tidal CO_2 , will be collected when available unless otherwise specified in table 1 below. If the patient is weaned from the mechanical ventilator during this time the time to weaning will also be recorded. Also, a chest x-ray will be obtained if the patient has not had one in the last 30 days. In addition, Critical Care Pain Observation Tool^{22,23} (CPOT) and Richmond Agitation & Sedation Scale^{24,25} (RASS) assessments will be administered prior to the electrical stimulation and every 6 hours during it. Patients will also be physically observed for any muscle twitching during the simulation period to try and determine if any other nerves were stimulated. Diaphragm thickness may be measured again at 24 and 48 hours or at the end of the stimulation period.

The ability of the pacing lead to accommodate neck movement and patient positional changes will also be assessed and logged during electrical stimulation.

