14.4 Review and Return of Completed Study Data

The investigator will maintain all source documents as required by the CIP, including laboratory results, supporting medical records, and signed Informed Consent forms. Sponsor and/or monitor will use source documents during the regular monitoring visits to verify data entered in the CRF. All CRFs will be reviewed for accuracy and the Principal Investigator will sign and date each completed CRF to document approval.

A copy of fully completed original CRFs will be made available to Sponsor.

Once all the subject data has been collected and verified, the analysis and reporting will be conducted. Any data existing for subjects who have not received treatment with PEPNS System will not be used in the analysis. Details of these subjects will, however, are referenced in the final report.

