An interim analysis of the primary endpoints may be done on the first 10 patients that were stimulated on both phrenic nerves. If they are met the secondary and other remaining analyses will also be performed. If not, the study will continue to enroll patients and all study endpoints and additional analyses will be analyzed when enrollment has been completed. If an interim analysis is done, the significance level used for testing will be 0.0125. At the final analysis (if needed) the significance level used for testing will be 0.0194. These levels were derived using a power cumulative error spending function with the parameter (rho) set to 1.0. This setting produces Pocock type boundaries (i.e. approximately equal spending for the two tests).

If an interim analysis is not done, the final analysis will use a significance level of 0.025 for testing the primary endpoints.

SECONDARY ENDPOINTS

The secondary endpoints are safety related and examine the percentage of patients who receive safe and successful placement of the multipolar lead in the left and right phrenic nerve utilizing ultrasound guidance and the percentage of patients who experience one or more serious device/procedure-related adverse events during the study.

- The percentage of patients who receive safe and successful placement of the multipolar lead in the left and right phrenic nerve utilizing ultrasound guidance will be determined.
- Phrenic nerve stimulation in synchrony with Mechanical Ventilation (MV) breaths will be measured to verify that it occurs with inspiration.
- The percentage of patients who experience one or more serious device/procedure-related adverse events during the study will be reported.

	PEPNS Study Statistical Analysis Plan	Document Number SAP0001	Rev. Level 1
<small>CONFIDENTIAL: THIS DOCUMENT AND ALL INFORMATION CONTAINED HEREIN IS PROPRIETARY TO STIMDIA MEDICAL, INC. AND IS NOT TO BE DISCLOSED WITHOUT THE EXPRESS WRITTEN PERMISSION OF STIMDIA MEDICAL, INC.</small>			

Safe and Successful Lead Placement

The percentage of patients who received safe and successful placement of the multipolar lead on the Left and right phrenic nerve utilizing ultrasound guidance will be evaluated in terms of the mean and standard deviation for preparation, placement, securement, removal and twitching. Twitching includes neck spasms, arm movement, shoulder movement on unwanted visible stimulation. This will be reviewed on a site basis, by neck circumference and BMI.

Adverse Events

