ECG (electrocardiogram) will be reviewed before during and after electrical stimulation to ensure electrical stimulation is not adversely affecting the heart. This will be evaluated by an expert in the reading of ECGs.

	PEPNS Study Statistical Analysis Plan	Document Number SAP0001	Rev. Level 1
CONFIDENTIAL: THIS DOCUMENT AND ALL INFORMATION CONTAINED HEREIN IS PROPRIETARY TO STIMDIA MEDICAL, INC. AND IS NOT TO BE DISCLOSED WITHOUT THE EXPRESS WRITTEN PERMISSION OF STIMDIA MEDICAL, INC.			

Table 3: Patient Vitals and PEPNS Data

Patient ID	Age (yrs)	Weight (kg)	Height (cm)	Body Mass Index (BMI)	IV Line (Y/N)	ET / Trach (E/T)	Neck circumference at the cricoid cartilage (cm)	Screening Blood Pressure	PEPNS System Lead Preparation	PEPNS System Lead Placement	PEPNS System Lead Securement	Lead Removal/ Skin Closure Assessment	Twitching?	Follow-up X-Ray Normal?	Adverse Events?	Device Malfunctions?
P03S01																
P04S01																
P05S02																
P06S02																
P07S02																
P08S01																
P09S02																
P10S02																
P11S01																
P12S02																
Mean																
Stdev																

ADDITIONAL EVALUATIONS

Briefly state the overall scientific objectives of the analyses, including the key unanswered questions that these analyses are designed to address. If necessary, provide additional detail to formulate the objectives in statistical terms. Include a brief summary of how each objective will be addressed in the analyses.

The clinical effect of electrical stimulation will also be examined for the following:

- Time to weaning from mechanical ventilation data.
- Diaphragm thickness at 0, 24 and 48 hours.

The period of time each patient was on ventilation before electrical stimulation and the time to wean will be reported. The number of attempts to wean the patient before and after electrical stimulation will also be reported, if available.

The trend in diaphragm thickness increase/decrease for each patient and the aggregation of patients will be evaluated over time. The trend in diaphragm thickness based upon its initial thickness will also be evaluated. Correlations in diaphragm thickness increase and neck circumference will also be reviewed.

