6. STATISTICAL METHODOLOGY

STATISTICAL PROCEDURES

The primary statistical methods used in this study will be descriptive where continuous variable will be summarized using means, medians, standard deviation, minimums and maximums and categorical variables will be summarized using frequencies and percent for each categorical level.

The primary endpoint will be analyzed using a logistic regression where diaphragm capture (yes/no) is the dependent variable and time point and subject are the independent fixed effect and random effect predictors. The point estimate of the diaphragm capture rate will be estimated from logistic regression model along with a two-sided 95% confidence interval. The lower bound of that confidence interval will be compared to the performance goal of 80%. If the lower bound is above 80%, then the endpoint will have been achieved.

Secondary endpoints will be summarized as noted in the secondary endpoints section. Each endpoint will be summarized descriptively.

Additional evaluations will also be summarized descriptively. In addition, diaphragm thickness over time will be modeled using regression analysis. The slope parameter and 95% confidence intervals will be presented. Additional diaphragm thickness analyses may be run.

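### The SAP evaluates the percentage of patients with safe and successful lead placement by means and SDs of five separate items, which do not determine that percentage

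*SAP*

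**What the plan says.** Protocol section 5.2 words the endpoint as "The percentage of patients who receive safe and successful placement of the multipolar lead in the left and right phrenic nerve utilizing ultrasound guidance". The Study Summary repeats it, and section 6.9 lists it as a safety endpoint with no formal hypothesis test. SAP section 2, under Secondary Endpoints, carries the same endpoint forward and says that the percentage will be determined.

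The only method is in the SAP paragraph on safe and successful lead placement. There the percentage "will be evaluated in terms of the mean and standard deviation for preparation, placement, securement, removal and twitching", to be reviewed by site, neck circumference and BMI. Table 3 has one row for each of patients P03 to P12. It has one column per step, including "Lead Removal/ Skin Closure Assessment" and a column headed *Twitching?*, and it ends with Mean and Stdev rows. It has no column for safe and successful placement, no left/right split and no n (%) row.

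SAP section 6 adds no further rule: "Secondary endpoints will be summarized as noted in the secondary endpoints section". Its general convention is that "categorical variables will be summarized using frequencies and percent for each categorical level". On what the items record, Protocol section 11.2 says only: "The ease of gain pacing lead access and setup will be assessed and logged". Neither document gives a scale or a cut-off.

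Three places bear on the denominator:
- Protocol section 14.4: "Any data existing for subjects who have not received treatment with PEPNS System will not be used in the analysis".
- SAP sections 2 and 3 make per protocol the primary analysis and intent-to-treat the secondary one. Section 2 applies both to the secondary endpoints and ties intent-to-treat to patients in whom treatment was attempted but aborted.
- Protocol section 6 and SAP section 2: the first two patients are stimulated on the left only, and the SAP keeps them for the safety analysis only.

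**The concern.** A percentage of patients needs a yes/no result for each patient and a stated denominator. The plan supplies neither. It gives a mean and SD for each of five items taken one at a time, with no rule for combining them within a patient. The endpoint requires both sides, but the Table 3 columns do not distinguish sides, so a patient with one successful lead would not stand out in the summary.

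Whether leads can be deployed under ultrasound guidance is among the things the study is meant to confirm (Protocol section 2, SAP section 2). If the SAP is followed as written, the report will hold five pairs of means and SDs and no answer to the endpoint. If a percentage is reported anyway, its definition will have been chosen after the placement data were seen.

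**Working it through.** The documents give no expected rate, power or significance level for this endpoint, so there is no planned figure to reproduce. The check is whether the planned summaries determine the endpoint.

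**Step 1. Endpoint and rule side by side.**

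| | Endpoint (Protocol 5.2, SAP 2) | Planned summary (SAP 2, Table 3) |
|---|---|---|
| Unit | Patient | Item |
| Result | Safe and successful, left and right | Five separate items, no side |
| Statistic | Percentage | Mean and SD |
| Success rule | Not defined | Not defined |

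**Step 2. If the items are ratings.** Inputs: n = 10 (rows of Table 3), plus an assumed 1 to 5 scale and an assumed success cut-off of 4 or above, since the documents give neither.
- Set A: 1,3,3,3,3,3,3,5,5,5. Sum 34, sum of squares 1 + 54 + 75 = 130.
- Set B: 1,1,4,4,4,4,4,4,4,4. Sum 34, sum of squares 2 + 128 = 130.
- Both have mean 3.4 and SD = √[(130 − 34²/10)/9] = √1.6 = 1.265. Success is 3/10 = 30% in A and 8/10 = 80% in B.

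The same happens at a higher mean. Sets 2,3,3,3,4,5,5,5,5,5 and 1,4,4,4,4,4,4,5,5,5 both have sum 40 and sum of squares 172. Mean is 4.0 and SD = √[(172 − 160)/9] = 1.155, yet success is 60% and 90%. Across every possible set of 10 such ratings there are 447 distinct mean/SD pairs. About 60% of them fit more than one percentage, and a cut-off of 3 or above also gives about 60%.

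**Step 3. If the items are yes/no.** Each item mean is then that item's proportion p. With five items, the share of patients successful on all five lies between max(0, 1 − 5(1 − p)) and p.
- p = 0.9: from 1 − 5 × 0.1 = 0.5 up to 0.9, so 50% to 90%.
- p = 0.8: from 1 − 5 × 0.2 = 0 up to 0.8, so 0% to 80%.

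Under either coding, the planned output leaves the endpoint undetermined.

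**Step 4. What a defined percentage would show.** The exact limits for x successes in n are the 0.025 quantile of Beta(x, n − x + 1) and the 0.975 quantile of Beta(x + 1, n − x). For illustration only, with n = 10:
- 10/10 = 100% (69.2% to 100%; lower limit 0.025^(1/10) = 0.692)
- 9/10 = 90% (55.5% to 99.7%)
- 8/10 = 80% (44.4% to 97.5%)

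One patient moves the estimate by 10 points, so which patients form N must be stated.

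**The case against.** The SAP does say the percentage will be determined. Its general rule for categorical data is frequencies and percent, and Table 3 lists patients one by one, so a count could be made once success is defined. The Mean and Stdev rows sit under a mixed table that also holds age, weight and BMI, and need not mean that every yes/no column will be averaged. The case report forms and Operator's Manual are not among the documents and may hold the item coding. The endpoint is secondary and descriptive in a feasibility study.

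Much of this stands. The percentage is not beyond reach: it could be derived from the patient-level data. That the step items are ratings is an inference, and Step 2 rests on an assumed scale. None of it removes the gap. An intention to determine a percentage is not a method, the one method stated is the wrong kind of summary, and no place in either document defines success for a patient.

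A reader might go further and infer that failed placements drop out through Protocol section 14.4, so that the result leans towards success. The documents do not support that. SAP sections 2 and 3 plan an intent-to-treat analysis that reaches the secondary endpoints and refers to attempted-but-aborted patients. Whether an aborted insertion counts as untreated under section 14.4 is not stated. The Table 3 identifiers run from P03 to P12 without a gap, and nothing shows that any placement failed. The handling of aborted attempts is unclear; it is not shown to be biased.

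**Conclusion.** The concern holds as a mismatch between an endpoint and its only stated analysis rule. The endpoint is a per-patient percentage for bilateral placement. The rule gives item means and SDs, which leave that percentage open by as much as 50 points in the rating example (30% or 80%) and 40 points in the yes/no example at 90% per item (50% to 90%). Those sizes depend on the assumed scale, cut-off and coding. That item summaries do not determine the percentage was found under both codings. The rule also conflicts with the SAP's own convention for categorical variables.

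No hypothesis test, power or error rate is involved. The change should be made because the endpoint cannot be reported as planned without a definition that is not yet written; it does not threaten the primary analysis.

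**What to change.** In SAP section 2, replace the mean/SD rule with a per-patient yes/no result. One workable definition is both leads placed under ultrasound guidance, capture shown at setup, and no serious device- or procedure-related event from placement. Other definitions are possible; what matters is that one is written down.

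- **Denominator:** all patients in whom bilateral placement was attempted, with aborted attempts counted as failures.
- **First two patients:** report them separately as left-side placement. They are left-only by design and must not be scored as bilateral failures.
- **Section 14.4:** state that its exclusion of untreated subjects does not remove attempted-but-aborted patients from this endpoint, in line with the intent-to-treat analysis in SAP sections 2 and 3.
- **Reporting:** n/N (%) with an exact 95% CI, and a matching column and row in Table 3.
- **Supportive data:** twitching as a count of patients, and the step items as frequency tables.

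The cost is SAP wording and one table, and no new data collection is apparent. The reported success figure may be lower if any attempt was aborted.

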2. BACKGROUND & RATIONALE

Ventilator-induced Diaphragm Dysfunction is a significant contributor to weaning difficulty in ventilated critically ill patients. It has been hypothesized that electrically pacing the diaphragm during mechanical ventilation may reduce diaphragm dysfunction resulting in faster weaning times.

Ventilator induced diaphragm dysfunction (VIDD) is considered a major determinant of the ability to successfully wean patients from mechanical ventilation¹. After as little as 18-69 hours of mechanical ventilation, autopsy specimens from brain-dead organ donors showed greater than 50% reduction in the cross-sectional areas of diaphragm myofibers² and animal models have shown a reduction of diaphragmatic force generating capacity proportional to the duration of mechanical ventilation^{3,4}. The hypothesis that electrically pacing the diaphragm could prevent VIDD has been previously proposed⁵. Surgically implanted systems for pacing the phrenic nerves and diaphragm have been used for the past 40 years in more than 2,500 adult and pediatric high-level spinal cord injury patients^{6,7} and in late-stage Amyotrophic Lateral Sclerosis patients. Implanted systems are not suitable for critically ill patients due to the invasive and complex surgical procedure^{8,9}. Brief transcutaneous stimulation of

phrenic nerves is often used for diagnostic purposes, but is not suitable for therapeutic purposes. Transvenous phrenic nerve stimulation (TPNS) has been periodically attempted over the past 50 years¹⁰. Stimdia has developed a novel percutaneous electrical phrenic nerve stimulation (PEPNS) system.

To evaluate the mitigating effect of phrenic nerve pacing on VIDD we have performed animal studies in canine, caprine and porcine models demonstrating that the operational parameters and insertion techniques chosen do not damage the surrounding tissue or nerves. Testing in animals has also demonstrated that the diaphragm strength is maintained in paced animals versus non-paced animals^{11,12}.

We hypothesize that beginning phrenic nerve pacing soon after initiation of deep sedation and mechanical ventilation will minimize the reduction in diaphragm strength over time in ventilated subjects and lead to faster weaning times. It has been shown that maintaining some level of work during sedation greatly reduces the deleterious decrease in diaphragm strength.

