6.7 Informed Consent Process

After a normal clinical assessment, the Principal Investigator may approach patients whom he or she feels may be suitable for entry into this clinical investigation. The Principal Investigator should introduce the patient or the patient's legally authorized representative to the clinical investigation by explaining the Clinical Investigation

Plan, procedures and objectives to the patient or his/her legally authorized representative. The Principal Investigator will then provide an information sheet describing the clinical investigation, potential discomforts, risks and benefits of participation. The patient or his/her legally authorized representative will have 24 hours to decide whether they wish to participate in this clinical investigation due to the criticality of the timing that the treatment is applied once the patient is on a mechanical ventilator.

Any queries that patients may have regarding this clinical investigation will be addressed appropriately by the Principal Investigator, or another member of the investigative team at the hospital. Patients or their legally authorized representatives will be instructed that they are free to obtain further information from the Principal Investigator at any time and that they are free to withdraw their consent and to discontinue their participation in the clinical investigation at any time without prejudice.

If the patient is willing to participate in the clinical investigation, he/she or his/her legally authorized representative must read, understand and sign the informed consent form. The Principal Investigator will also sign this at the same occasion. Two copies of the consent form will be made. The original signed consent form will be kept in the Investigation Site File. A copy will be kept in the subject's medical notes and a further copy provided to the subject or his/her legally authorized representative.

Since the subjects will be unconscious and mechanically ventilated at the time of the informed consent process should they regain consciousness they will be allowed to withdraw from the study if desired without any impact on their medical treatment. If subjects do regain consciousness during the treatment they will be asked to sign the informed consent form if they are able.

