6.15 Additional Study Data

Time to weaning from mechanical ventilation data will be collected and reported.

The effect of electrical stimulation on diaphragm thickness, blood gas parameters, vital signs, end tidal CO₂ and tidal volume may be characterized. To this end, stimulation will be stopped for a single period of 1 hour within the middle period of the 6 hour blood gas analysis collection period, when the patient has been deemed to be hemodynamically stable by the attending physician. Data will be collected on blood gasses, pulse rate, blood pressure, SpO₂, end tidal CO₂ and tidal volume at the end of the 1 hour period. This data will be used to characterize the effect of electrical stimulation on hemodynamics. The mode of ventilation will also be recorded because stimulation is predicted to have little effect on tidal volume in flow controlled modes whereas it is predicted to increase in pressure control modes of ventilation. Tidal volume may also be adjusted to be the same as when electrical stimulation was turned on to eliminate any confounding effects of decreased minute and tidal volumes when stimulation is turned off. All other parameters such as breath rate, PEEP, FIO₂ etc. will be kept the same.

The diaphragm thickness may be measured prior to the stimulation, at 24 hours and at 48 hours or after the completion of all of the stimulation using ultrasound when clinically feasible, i.e., 0 hours, 24 hours and 48 hours or end of stimulation.

7. PROCEDURAL GUIDELINES (Treatment Procedure)

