12. DATA RECORDING AND SUBMISSION REQUIREMENTS

Data

All aspects of the study will maintain patient privacy and be Declaration of Helsinki and General Data Protection Regulation (GDPR) and Data Protection Act 2018 compliant.

All **raw data** will be entered into an Excel or validated spreadsheet format (with patient names excluded) and include all data collected on the patients up to the time the data is frozen including baseline, procedure, and all follow up data available. All data sets provided shall be clean with all queries resolved.

The following are the types of data in the study:

RAW DATA:

1. PEPNS System electronic archive – data recording by the PEPNS system will be electronically archived by Stimdia Medical.
2. Patient history file – this document will confirm patient meets inclusion and exclusion criteria while also documenting all demographic and physiology aspects of the enrolled patient.
3. PEPNS System procedure report – documentation of procedure related information, e.g., sedation, ventilation, stimulation, ultrasound, test article documentation, procedure step checklist and procedure related specifics noted.

CASE REPORT FORMS (CRF):

1. Screening form
2. Index procedure form
3. Adverse event form
4. Patient disposition form
5. Protocol deviation form
6. Device malfunction form
7. Follow up form

SPREADSHEET AND ANALYSES:

1. All data relevant to analysis will be maintained in a validated Excel spreadsheet until the completion of the study. The master spreadsheet will be validated and maintained by Stimdia Medical. All Excel files used for the data analysis must be password protected and only authorized study personnel can have access to the passwords.

Interim analysis and results will be reviewed with the steering committee in a periodic manner.

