The percentage of patients who experience one or more serious device/procedure-related adverse events during the study will be reported. The evaluation results for the follow-up x-ray will also be noted.

Stim and Vent Synchrony

The phrenic nerve stimulation in synchrony with Mechanical Ventilation (MV) breaths will be measured to verify that it occurs with inspiration over all of the stimulated breaths for each of the patients. The synchrony on the detection of inspiration and expiration will be compared against the user set trigger flow section and compared to a fast trigger time which has been reported as 88 msecs.

Related Evaluations

Critical Care Pain Observation Tool (CPOT) assessments are made on all patients enrolled and will be reported before during and after stimulation on all patients. The pain assessment tool, CPOT, is based on four domains: the patient's facial expressions, body movements, compliance with ventilator (or voice use for non-intubated patients), and muscle tension. Each domain has a possible score of 0 to 2. The total score can vary between 0 and 8, where 0 indicates no pain behavior and 8 indicates clear signs of pain behavior.

Richmond Agitation and Sedation Scale (RASS) scores will be reported on all patients. The RASS measures agitation and sedation level, the score ranging from +4 to -5, where a score of 0 indicates an awake and adequate patient. Scores from -1 to -5 indicate an increasingly sedated patient, and scores from +1 to +4 indicate an increasingly irritable and agitated patient.

The CPOT and RASS scores will be evaluated to determine that the stimulation does not cause pain to the patient.

An assessment will be made to determine the sensitivity of the lead to patient position. Patient will be repositioned every 2 to 4hrs per hospital protocol and disease diagnosis requirements. Leads will be disconnected from the electrical stimulator using the extension lead during these non-stim periods. Reestablishing stimulation after reconnection will be evaluated along with the ability of the system to handle patient repositioning.

Vitals signs and blood gasses will be evaluated to determine if electrical stimulation does not have an untoward effect on patient. This will be evaluated by an expert in ICU ventilation / blood gas analysis.

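### The SAP plans to conclude from CPOT and RASS that stimulation causes no pain, but does not read CPOT by concurrent RASS and has no score in the planned 1-hour off period

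*SAP*

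**What the plan says.** SAP section 2, Related Evaluations, describes CPOT as four behavioural domains (facial expression, body movement, ventilator compliance, muscle tension) with a total of 0 to 8. RASS runs from +4 to -5, with negative values meaning deeper sedation. The purpose is then given: "The CPOT and RASS scores will be evaluated to determine that the stimulation does not cause pain to the patient". No threshold, contrast or decision rule follows. The same subsection says that CPOT assessments "will be reported before during and after stimulation on all patients".

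Protocol section 11.2 sets the schedule: CPOT and RASS "assessments will be administered prior to the electrical stimulation and every 6 hours during it". Table 1 in section 11.3 lists them under the index procedure only, with no times.

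Protocol section 6.15 says that "stimulation will be stopped for a single period of 1 hour". For the end of that hour it states: "Data will be collected on blood gasses, pulse rate, blood pressure", followed by SpO2, end-tidal CO2 and tidal volume. CPOT and RASS are not on the list.

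On sedation, the rationale in protocol section 2 speaks of pacing begun "soon after initiation of deep sedation and mechanical ventilation", and section 6.7 opens its last paragraph with "Since the subjects will be unconscious and mechanically ventilated at the time of the informed consent process". Section 12 describes the procedure report as "documentation of procedure related information, e.g., sedation, ventilation, stimulation", among other items.

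**The concern.** The stated aim presumes its answer: the scores are to be evaluated to determine that there is no pain, not whether there is. The instrument observes behaviour, and sedation suppresses behaviour. Without a rule that ties each CPOT to the depth of sedation when it was taken, a run of low scores in deeply sedated patients would read the same as a run of low scores in patients who could have reacted.

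A within-patient comparison of stimulation on and off would help, because background sedation and illness are more alike across one hour than across two days. The protocol already contains such a period but uses it only for physiology and tidal volume.

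At stake is a tolerability statement about a first-in-human device. Pain is a listed device or procedure risk (protocol section 13.1), and the study is meant to help define a pivotal study (section 13.3), so an unqualified statement could be carried forward.

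**Working it through.** The documents attach no figure to the pain evaluation, so there is none to reproduce. The check is a comparison of what is reported with what is scheduled, and then a reading of what the scores can show.

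**1. Schedule.** Maximum stimulation is 48 hours (protocol section 6), with scores every 6 hours (section 11.2).

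| Condition | Protocol | SAP section 2 |
|---|---|---|
| Before stimulation | Scheduled, number not stated | CPOT reported |
| During stimulation | 48/6 = 8 over a full 48 hours, fewer if it ends early | CPOT reported |
| 1-hour off period (6.15) | 0 scheduled | Not mentioned |
| Disconnection for repositioning | 0 tied to it | Disconnection described, no score tied to it |
| After stimulation ends | 0 scheduled | CPOT reported, time and number not stated |

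Two findings follow. The SAP's after-stimulation CPOT has no protocol time point. Once stimulation has started, no score is planned for a stimulation-off moment until that unscheduled one.

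**2. What a low CPOT shows.** All four domains need a patient able to display behaviour. The SAP's own description of RASS says that scores from -1 to -5 mark increasing sedation, so the information needed to judge whether a CPOT is informative is collected at the same times. The SAP reports both scales but specifies no cross-reading of one by the other, and no count of the CPOT scores taken while behaviour could be seen.

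**3. What a raised CPOT shows.** SAP section 2, under Safe and Successful Lead Placement, includes neck spasms and arm or shoulder movement in its definition of twitching. Such movements could be scored under body movement or muscle tension, or disturb ventilator compliance, with no pain present. Twitching is recorded separately, but the plan does not link it to CPOT.

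**4. What the existing contrast offers.** Before versus during is a comparison of off with on. But the later on-stimulation scores are up to 48 hours from the baseline, over which sedation may differ. Scores just before and at the end of the off hour would be about one hour apart. That comparison bears on both the problem in step 2 and the one in step 3, although it does not remove the floor effect in a patient too sedated to react in either state.

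**The case against.** The strongest reply is that sedation is not ignored. RASS is a sedation scale, the challenged sentence evaluates it together with CPOT, and sedation is documented in the procedure report. This stands, and it limits the point: what is missing is a rule for using RASS to interpret CPOT, not a measure of sedation.

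It can also be said that deep sedation is the expected setting and not an eligibility requirement. Protocol section 6.7 foresees patients regaining consciousness, and section 2 foresees weaning trials within the 48 hours. That is correct. Some scores may be fully informative, which is a reason to identify and count them.

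Other signals exist: adverse events are recorded whatever their cause, twitching is observed, and pulse and blood pressure are taken in the off hour. They soften the gap but do not support the sentence as worded.

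On the remedy, SAP sections 7 and 8 describe a 10-patient cohort in the past tense, so new bedside scores may be unobtainable for those patients. In addition, tidal volume may be adjusted in the off hour, which could affect the ventilator-compliance item. Both are fair and are reflected in the fix.

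A reader might infer more than the documents support:
- That the plan will show no pain whatever the truth. Twitching could push CPOT upward, so the net direction is not established.
- That lead insertion separates the baseline score from the rest. Section 11.2 says only that scoring precedes stimulation, so the baseline may follow insertion.
- That a patient who reacts is given more sedation before the next score. No section says so.

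**Conclusion.** The point holds as a matter of interpretation and scheduling. CPOT is not read by concurrent RASS, the off hour carries no CPOT or RASS, the SAP's after-stimulation CPOT has no matching protocol time, and the conclusion is worded as already reached. In heavily sedated patients a low CPOT is weak evidence of no pain, and a raised one may reflect evoked movement.

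The size is modest. This is a descriptive evaluation placed with the secondary endpoints. It is not itself an endpoint, no hypothesis test is attached to it, and the primary endpoints are untouched. A chance of missing real pain cannot be given from the documents: it would need a true pain rate and a detection rate under sedation, and neither is stated.

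The conclusion assumes that the expected sedation described in protocol sections 2 and 6.7 applies to a material share of the scores. If most scores were taken in patients able to react, the tabulation proposed below would show it and the tolerability statement would be stronger.

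**What to change.** 1. **SAP, Related Evaluations.** Tabulate every CPOT by the RASS taken at the same time. State in advance the RASS levels at which behaviour is considered observable (the documents give none, so the trial team must set and justify them), and report how many scores fell there. Replace the present aim with a descriptive statement limited to those scores. This uses planned data and costs only wording and one table.

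2. **Protocol sections 6.15 and 11.2, for any patients still to be enrolled.** Score CPOT and RASS just before and at the end of the existing 1-hour off period. Report the paired on-versus-off difference descriptively, noting any tidal volume adjustment. The cost is two bedside assessments per patient by staff already scoring every 6 hours, and a protocol amendment.

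3. **Reconcile the after-stimulation score.** Either give it a time point in the protocol or remove it from the SAP. If it is kept, pair it with a RASS. The cost is one further assessment at most.

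Changes in sedatives or analgesics may be listed beside the scores where recorded. They should not be counted as pain responses, since they may be made for other reasons and the protocol does not show that timed doses are captured.

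The main downside is a narrower tolerability claim. If enrolment is complete, item 1 and the wording part of item 3 can still be carried out.
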